2.8 Randomization

789

790

791

792

793

794

795

796

797

798

799 800

801

802

803

804 805

806

807

808

809

813

Randomization will occur within 7 days after the participant has met all eligibility criteria (Section 2.2), completes prism adaptation testing (Section 2.6), and meets the randomization criteria (Section 2.7).

Participants eligible for randomization will be randomly assigned with equal probability to one of the following groups:

- Prism group: spectacles with refractive correction (if required) and relieving prism as outlined in table 1 (see section 3.1)
- Non-prism group: spectacles with refractive correction (if required) and no prism
- The Jaeb Center will construct a separate Master Randomization List using a permuted block design stratified by mean distance control score (2 to <3, 3 to <4, 4 to 5). A participant is
- officially randomized when the website randomization process is completed.

3.1 Treatment for Prism Group

Participants assigned to the prism group will be prescribed spectacles with base-in prism ground into each lens. Total prism prescribed will be equal to 40% of the largest deviation at distance or near measured by PACT, with the total prism divided equally between the two lenses (Table 1). The prism spectacles must be worn all waking hours. No IXT treatment other than the prism spectacles can be prescribed for the duration of the study. Refractive correction will be prescribed according to criteria in section 3.3.

Table 1: Prescribed Prism According to Maximum Exodeviation

Maximum exodeviation by PACT (Larger Value of Distance or Near)	Total Base-in Prism Magnitude*	Base-in Prism Magnitude for Each Eye
16Δ	6Δ	3Δ
18Δ	7Δ	3.5∆
20Δ	8Δ	4Δ
25Δ	10Δ	5Δ
30∆	12Δ	6Δ
35Δ	14Δ	7Δ

^{*}Total prism is 40% of the larger exodeviation comparing the distance and near PACT.

3.2 Treatment for Non-prism Group

Participants in the non-prism group will be prescribed non-prism spectacles according to refractive error correction criteria in section 3.3. No IXT treatment other than non-prism refractive correction can be prescribed for the duration of the study.

3.3 Post-Randomization Criteria for Refractive Error Correction

All participants in the study will be wearing spectacles following randomization and all those who habitually wore spectacles pre-study will be provided new spectacles for masking purposes (paid for by the study). All participants in both groups will be prescribed spectacles to correct their refractive error (or plano as appropriate) and those in the prism group will also have prism incorporated.

Refractive error correction for new spectacles for both groups will be calculated automatically by the study website and will meet all of the following criteria:

- Fully correct astigmatism (if present)
- If less hyperopic eye has SE myopia:
 - o Prescribe the full sphere in both eyes
- If less hyperopic eye has SE hyperopia or emmetropia:
 - After correction of astigmatism, prescribe sphere so that spectacles will have plano
 SE in the less hyperopic eye
 - o Match any reduction of sphere made to the less hyperopic eye in the fellow eye
- Prism (if in prism group) will be split equally between eyes (see section 3.1)

Participants in both groups must wear their refractive correction all waking hours.

NOTE: Because the study is providing spectacles to all randomized participants, those with any degree of refractive error (astigmatism, myopia, or anisometropia) will be prescribed spectacles with some refractive correction. Only participants who have no refractive error or have pure spherical hyperopia that is equal between both eyes will be prescribed plano lenses.

3.4 Follow-up Visit Schedule

The follow-up visit schedule is timed from randomization as follows:

- Telephone call: 3 weeks (21 to 28 days) after randomization to check that the spectacles have been dispensed/received and that the participant is wearing the new spectacles
- Outcome Visit: 8 weeks (±2 weeks) after randomization

Additional visits may be scheduled at investigator discretion although no data will be entered on the website.

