1.14 Study Objective

The objective of this short-term, pilot randomized trial comparing spectacles with relieving prism to spectacles without prism is to determine whether to proceed to a full-scale, longer-term randomized trial. This decision will be based primarily on assessing the initial (8-week) response to prism by comparing treatment groups on the following outcomes:

- Mean distance IXT control score (the mean of 3 control scores) (primary outcome)
- The proportion of participants demonstrating a "treatment response," defined as ≥1 point improvement in the mean distance IXT control score without spontaneous exotropia during control testing (secondary outcome)
- The proportion of participants reporting adverse effects and good/excellent spectacle wear compliance

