Additional Eligibility Criteria for Randomization Based on Prism Adaptation Testing

- Exodeviation by PACT while wearing "trial" relieving prism for 30 minutes is smaller at distance or near than measured during initial testing (e.g. not fully adapting to prism at both distances)
- No new esotropia on cover test at near while wearing "trial" relieving prism for 30 minutes, compared with enrollment measurement taken without prism
- No esodeviation $>6\Delta$ on PACT at near while wearing "trial" relieving prism for 30 minutes

Sample size

- 410 Up to 100 participants will be enrolled for same-day prism adaptation testing until up to 64 411 participants meeting the randomization eligibility criteria based on the prism adaptation test are 412 randomized (32 per treatment group).
- 414 Treatment Groups
- Als Randomization (1:1) to the following groups:
- Prism Group: Spectacles with refractive correction AND base-in relieving prism (40% of the greater of the exodeviation by PACT at distance or near) equally divided between the 2 lenses

• Non-prism Group: Spectacles with refractive correction (or plano spectacles if no significant refractive error) and no prism

421 422

424

Visit Schedule

- Enrollment Visit
 - If eligible, Randomization (same day as enrollment visit or within 7 days)
- 3-week phone call (21 to 28 days) after randomization
 - Outcome Exam: 8 weeks (± 2 weeks) after randomization

426 427 428

429

Testing Procedures

Distance and near control of IXT (3 measurements), near stereoacuity, distance and near cover test, and distance and near PACT will be measured by a study-qualified examiner at enrollment, and by a Masked Examiner at 8 weeks. The prism adaptation test will be assessed by a study-qualified examiner at enrollment. Distance visual acuity, fusional convergence amplitude, and suppression will be assessed by a study-qualified examiner at both visits. In addition, symptoms of headache, eye strain, dizziness, nausea, and problems with spectacle wear will be assessed at both visits.

437 438

Primary Analysis

• A comparison of mean distance control scores (mean of 3 assessments over the exam) between the prism group and the non-prism group at 8 weeks.

440 441 442

443

444

445

446

439

Secondary Analyses

- A comparison of the proportion of participants showing a "treatment response," defined as an improvement of ≥1 point in distance control (mean of the 3 assessments over the exam) between enrollment and 8 weeks.

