Historical information elicited will include the following: date of birth, sex, race, ethnicity, cycloplegic refraction, prior treatment for IXT, spectacle correction, and medical history.

565 566 567

568

569

570

564

2.4 **Testing at the Enrollment Exam**

All testing must be performed with the participant wearing "habitual correction" (with spectacles if child currently wears spectacles or without spectacles if child is not wearing spectacles).*

571 572 573

574

575

* The exception is for a participant who does not require spectacles per IXT6 protocol but is wearing a pair of spectacles that do not meet pre-enrollment spectacle tolerances (see section 2.2). This participant can have enrollment testing performed with or without these spectacles, provided the visual acuity eligibility criteria are met (see section 2.2). If visual acuity criteria are not met, the child is not eligible at that visit.

576 577 578

There is no specified "waiting" time that needs to occur between enrollment measurements. although testing must be performed without cycloplegia and in the following specified order at the enrollment visit:

580 581

582

579

1. Spectacle Prescription Verification (Lensometry):

583 584 Prior to performing the enrollment examination, the participant's habitual spectacle correction (if worn) is to be verified using a lensometer and compared with study spectacle requirements using procedures outlined in the IXT6 Testing Procedures Manual

585 586 587

2. Symptom and Spectacle Surveys:

588 589

A brief survey of IXT symptoms will be administered to the child. Response options are based on frequency of observations: never, sometimes, and all the time.

590 591 592 • A brief survey of symptoms that may be associated with prism spectacle wear such as headaches, eye strain, and problems with spectacle wear will be administered to the parent of the participant. Parents are asked to respond to the survey questions based on their observations of their child in the past 2 weeks. Response options are based on frequency of observations: never, rarely, sometimes, often, always, and not applicable.

593 594

595

596

597

STEPS 3 through 8 must be performed in the specified order by the same study-certified examiner (pediatric ophthalmologist, pediatric optometrist, or certified orthoptist) on the same day and without cycloplegia.

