 \circ 1 Δ base up right lens, 1 Δ base down left lens

o No prism right lens, 1Δ base in left lens

• Examples within tolerance:

 \circ 2 Δ base down both lenses

• Examples NOT within tolerance:

948

949 950

951

952

953

954

955

29May2019

992 at distance (6 meters) and near (1/3 m) as outlined in the IXT6 Testing Procedures Manual.

9. Control of the Exodeviation #3 (Masked, see item #4)

• The same masked examiner who assessed IXT Control #1 & 2 does this third measure of control.

10. Fusional Convergence Amplitude Testing

- Testing must be performed by a pediatric ophthalmologist, pediatric optometrist, or certified orthoptist.
- Convergence amplitudes will be measured at distance
- Using the PEDIG-approved IXT6 prism bar, record the blur, break, and recovery points according to the IXT6 Testing Procedures Manual.

11. Suppression:

993

994

995

996

997 998

999

1000 1001

1002

1003

1004

1005

1006 1007

1008

1009

1010 1011

1014 1015

1020

1021

1022

1023 1024

1031

- Testing must be performed by a pediatric ophthalmologist, pediatric optometrist, or certified orthoptist.
- Assessment of suppression at distance using the Suppression Scale and procedures outlined in the IXT6 Testing Procedures Manual.

12. Distance Visual Acuity Testing:

• Monocular distance visual acuity testing without cycloplegia will be measured using the same method used at enrollment.

3.8 **Additional Visits**

1012 Investigators may schedule additional visits at their discretion, although no data will be entered 1013 on the website

3.9 **Surgical or Non-Surgical Treatment**

Strabismus surgery and non-surgical treatments for IXT, other than the study-prescribed 1016 1017 spectacles, are not allowed during the study. If the investigator feels that additional treatment 1018 is needed outside of study guidelines, please contact a study chair for further clarification. 1019

Treatment of Amblyopia

Given the exclusion of participants with amblyopia and the short duration of the trial, no treatment for amblyopia is allowed during the study.

Management of Refractive Error

1025 Because of the short duration of the study, the spectacles prescribed at randomization may not be changed or discontinued without contacting a protocol chair. 1026 1027

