4.3.3 Risk Assessment

1072 It is the investigators' opinion that the protocol's level of risk falls under DHHS 46.404, which is 1073 research not involving greater than minimal risk.

1074 1075

4.4 **Reporting Adverse Events**

1076 Although no adverse events are anticipated as a result of prism therapy or non-prism spectacle 1077 wear, any new cases of amblyopia or new cases of constant esotropia will be reported. No

surgical procedures are part of the protocol and no treatments are being prescribed that are not part of usual care. Investigators will abide by local IRB reporting requirements.

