5.2.1 Decision Guideline for Determining Whether to Proceed to a Randomized Trial

The data collected in this short-term, pilot randomized trial will primarily be used to determine whether to proceed to a full-scale, longer-term randomized trial of prism vs. non-prism. A decision guideline has been developed to aid in this decision (see below). The side effect profiles in each treatment group will also be considered when deciding whether to proceed with a full-scale trial.

1148 1149 1150

1151

1152 1153

1154

1155

1156

1157

The decision guideline for determining whether to proceed to a full-scale randomized trial will be based on the primary analysis estimate of the treatment group difference in mean distance control scores at 8 weeks. The standard deviation of 8-week distance control in IXT3 was 1.5 points (95% CI = 1.2 to 1.8 points). The convenience sample of 64 participants yields relatively low statistical power (61%) for detecting a difference if the true difference = -0.75 assuming an SD in the current study of 1.5 points and accounting for up to 5% loss to follow up. As the statistical power is poor, the decision guideline was based solely on the size of the observed difference in mean control scores (prism – non-prism). The decision is:

- **Proceed** if the observed difference < -0.75 points 1158
- 1159 • Uncertain if the observed difference favors the prism group by less than 0.75 points (diff <0 1160 and > -0.75)
- 1161 • **Do not proceed** if the observed difference is zero or favors the non-prism group (diff ≥ 0)

1162 1163 1164

*Note that differences (prism – non-prism) favoring prism will be negative given that lower control scores indicate better control.

1165 1166

1170

1171 1172

1173 1174

1175 1176

1177 1178

1179 1180 1181

1182 1183

1184

1185

1186 1187

1188

1189

1190

1191 1192

1193 1194 1195

1196 1197

1201

Decision Guideline #1: Whether to Proceed to	TRUI	(Prisn	nent Gro 1 – Non- in point	. ,	erence
Full-Scale Randomized Trial Based on OBSERVED Difference in Means in Pilot Study	-0.25	-0.50	-0.75	-1.0	-1.25
Proceed** if observed difference is ≤-≤0.75	11%	27%	50%	73%	89%
Uncertain if observed difference is <0 and > -0.75	62%	62%	46%	26%	11%
Do not proceed if observed difference is ≥0	27%	11%	4%	1%	0%

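### No data from additional visits may be entered, so non-reportable side effects seen only there that settle before the 2-week parent recall, or are followed by withdrawal, have no stated route into the side effect profile

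*Protocol*

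**What the plan says.** Protocol 3.4 fixes two contacts after randomization, a 3-week telephone call and the 8-week outcome exam, and then adds: "Additional visits may be scheduled at investigator discretion although no data will be entered on the website". Section 3.8 repeats the rule: "Investigators may schedule additional visits at their discretion, although no data will be entered". Section 4.8 makes the electronic case report forms the source data.

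Side effects have a named role in the decision that the pilot is meant to inform. Section 1.14 lists among the outcomes compared between groups: "The proportion of participants reporting adverse effects and good/excellent spectacle wear compliance". Section 5.2.1 adds: "The side effect profiles in each treatment group will also be considered when deciding whether to proceed with a full-scale trial".

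The scheduled collection is narrow. In section 1.15, "symptoms of headache, eye strain, dizziness, nausea, and problems with spectacle wear will be assessed at both visits", meaning enrollment and 8 weeks. For the parent survey (sections 2.4 and 3.7), "Parents are asked to respond to the survey questions based on their observations of their child in the past 2 weeks". SAP 4.5 describes survey item scores at those same two visits and names no other source.

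Section 4.4 provides a separate reporting route for two conditions: "any new cases of amblyopia or new cases of constant esotropia will be reported".

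**The concern.** A child who is brought back between randomization and 8 weeks may well have been brought back because of the spectacles. What the investigator learns at that visit has already been obtained, yet the protocol directs that it not be entered. The side effects that the protocol itself expects are of the kind this rule would lose. Section 4.3.2 says that prism may cause eye strain or distortion, which usually fade with time or when the spectacles come off. A symptom that appears early, prompts a visit and fades can be over before the parent survey's 2-week window opens.

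At stake is whether the tolerability information used in the decision to proceed covers the treatment period or mainly its last 2 weeks. Section 1.13 makes a full-scale trial conditional on the absence of significant adverse effects as well as on a reasonable response, so early tolerability is part of what the pilot is for.

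**Working it through.** The plan gives no figure for this point: no visit rate, no expected side effect rate and no threshold for side effects. The check is therefore a trace of each route by which a side effect could reach the analysis, plus one calculation of how much wear time the parent survey covers.

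**Routes into the data**

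- *8-week exam (3.7).* Child and parent surveys, compliance rating, masked cover test and PACT at distance and near, and visual acuity are all recorded. A problem still present at 8 weeks reaches the database.
- *Child survey (2.4, 3.7, 5.5.7).* No recall window is stated, so an earlier symptom could be mentioned. However, this survey asks about symptoms of intermittent exotropia. Symptoms linked to prism wear are asked of the parent.
- *Section 4.4 reports.* New amblyopia and new constant esotropia are covered, and reporting is not limited to the 8-week exam. Eye strain, distortion and non-constant esotropia are not named. Neither protocol 5.5 nor the SAP describes a table of these reports.
- *3-week call (3.5, 4.1).* Section 4.1 has the site ask about concerns. Section 3.5 lists as items to record only the date of spectacle receipt, non-receipt and the factors behind a delay.
- *Spectacle change or stop (3.11).* A protocol chair must be contacted, but no data item or analysis is attached to that contact.
- *Compliance (5.5.9, SAP 5.3).* The amount of wear is recorded, but not the reason for reduced wear.
- *Withdrawal (4.2).* The investigator tries to learn the reason. No analysis of reasons is described, and the child has no 8-week survey.
- *Additional visit (3.4, 3.8).* Nothing is entered.

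This leaves a side effect outside section 4.4 that is seen only at an additional visit and either resolves before the last 2 weeks or is followed by withdrawal.

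**Wear time covered by the parent survey**

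Inputs: recall of 2 weeks (2.4, 3.7); outcome exam at 8 ± 2 weeks, so week 6 to 10 (3.4); spectacle receipt at week 0 to 3 after randomization. The receipt range is an assumption, because the documents give no expected dispensing delay.

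Share covered = 2 / (exam week − receipt week). Weeks outside the recall = exam week − receipt week − 2.

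| Exam week | Receipt week 0 | Week 1 | Week 2 | Week 3 |
|---|---|---|---|---|
| 6 | 33% (4 weeks outside) | 40% (3) | 50% (2) | 67% (1) |
| 8 | 25% (6) | 29% (5) | 33% (4) | 40% (3) |
| 10 | 20% (8) | 22% (7) | 25% (6) | 29% (5) |

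Coverage runs from 2/(10 − 0) = 20% to 2/(6 − 3) = 67%, leaving 1 to 8 weeks outside the recall.

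**Children without an 8-week survey**

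Section 5.1 allows up to 5% loss to follow-up: 64 × 0.05 = 3.2, or about 3 children across both groups. This is the plan's allowance for all losses. It does not estimate losses caused by side effects.

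**The case against.** The strongest case on the other side is that the important events are already covered. The most serious form of overcorrection, a new constant esotropia, is reportable whenever it is found, as is new amblyopia. Anything that persists is recorded at 8 weeks. Spectacles cannot be changed or stopped without contacting a chair. What remains is transient, and transient symptoms bear least on a decision whose numerical guideline uses only the observed difference in control scores. Data from discretionary, unmasked visits would also carry their own ascertainment bias, so leaving them out is a defensible choice. Finally, the 2-week recall affects every child, whereas a form for additional visits reaches only those who return.

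Much of this stands. A reader might infer that problems prompting an early visit can never enter the data, or that the rule hides early overcorrection from safety review. The documents do not support either reading, because of the routes through section 4.4 and the 8-week exam. Nor is the no-entry rule a contradiction of section 4.4: it concerns website entry of visit data and does not forbid those reports.

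A reader might also infer that the rule makes prism look better tolerated than it was. This is plausible, since section 4.3.2 links eye strain and distortion to prism, but it is not shown. Both groups receive study spectacles with newly calculated refractive correction, so problems can arise in either. Screening (2.7) also removes children with new near esotropia, or a near esodeviation above 6Δ, in the same amount of prism.

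What does not stand is that the other routes close the gap. None gives a transient, non-reportable side effect a stated place in the analysis. The ascertainment problem is a reason to report such data descriptively, not a reason to bar them.

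**Conclusion.** The point holds in a narrow form. Non-reportable side effects that are seen only at an additional visit, and that resolve before the parent's 2-week recall or are followed by withdrawal, have no stated route into the side effect profile named in sections 1.14 and 5.2.1. The reports under section 4.4 also lack a stated table.

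The window in which such events can be missed is 1 to 8 weeks of the time since spectacle receipt, given receipt at weeks 0 to 3 and an exam at weeks 6 to 10. How many children are affected, and whether the loss falls more on one group, cannot be determined because the documents give no rate of additional visits or side effects. An effect on the decision to proceed is possible but not demonstrated, since side effects enter that decision without a numerical criterion. This is an inexpensive improvement to data capture. It leaves the primary comparison unaffected.

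**What to change.** In protocol 3.4 and 3.8, replace the no-data rule with a short form for each additional visit. It should record the date, the reason for the visit, symptoms reported, any new esotropia if a cover test was done, and any change or stopping of the spectacles with the reason. No procedure is required at the visit; the form records only what was found.

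In SAP 4.5, add a descriptive count by group of participants with at least one additional visit for a spectacle or eye problem, shown together with the section 4.4 reports of new amblyopia and new constant esotropia. Give counts and percentages with no test. State that the visits are unmasked and discretionary, so a difference between groups may partly reflect who was brought back and by which sites.

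The cost is one short form page for the children who have such visits and a small addition to one table. No visit, staff or procedure is added, and clinical management does not change. The form does not close the recall gap for children who have a transient problem and do not return, and the report should say so.
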